3. TREATMENT PLAN

Treatment will be administered primarily on an outpatient basis, although may be given inpatient based on location or status of patient. Reported adverse events and potential risks are described in Section 7. Appropriate dose modifications are described in Section 6. No investigational or commercial agents or therapies other than those described below may be administered with the intent to treat the patient's malignancy.

Each cycle will begin with ANC >1000 and platelet count >100 without transfusion support. At the beginning of each cycle pregnancy testing must be confirmed negative for females of child bearing potential and counseling regarding pregnancy risks must be confirmed for all patients

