
A: Dose as assigned; administration schedule
 
B: Dose as assigned; administration schedule
 
a: Albumin, alkaline phosphatase, total bilirubin, bicarbonate, BUN, calcium, chloride, creatinine, glucose, LDH, phosphorus, potassium, total protein, SGOT [AST], SGPT [ALT], sodium.
 
b: Serum or urine pregnancy test (women of childbearing potential). Obtain 10-14 days prior to study enrollment and again within 24 hours prior to Day 1 of each cycle. Obtain weekly during cycle 1. Females with irregular menstruation must have a pregnancy test every 14 days while receiving protocol therapy (including breaks in treatment). Pregnancy test is also required if patient misses her period or has unusual menstrual bleeding. Pregnancy testing must also occur at Day 28 (and at Day 14 if female has irregular menstruation) after lenalidomide discontinuation).
 
c: Continue pattern of measurements while on study.
 
d: Off-study evaluation
 
e: As indicated based on diagnosis and tumor location.

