Statistical analysis will be conducted at the completion of the study after accrual goals have been met. We will describe the baseline demographic and clinical characteristics, adverse events and response in all patients. Continuous variables will be summarized using mean, standard deviations, median, maximum and minimum values. Discrete variables will be summarized using counts and percentages with the corresponding 95% confidence intervals where appropriate. Time to event variables will be analyzed using Kaplan Meier methods. Progression free survival (PFS) and overall survival rates and the corresponding confidence intervals at fixed time points will be derived from the Kaplan Meier estimate. PFS will be defined as the time between date of first dose of the study therapy and date of progression or death, whichever occurs first. Patients will be censored on the date of last tumor assessment if they remain alive and do not have tumor progression. Surviving patients who did not receive any on-treatment tumor assessment will be censored on the date of first dose of study medication. A window of 1 week prior to the PFS rate time points will be applied to account for different tumor assessments dates, since not all patients adhere to scheduled dates. Descriptive statistics will be used to summarize time to event endpoints, if Kaplan Meier methods fail to provide estimates. All statistical analysis will be performed using SAS software version v 9.3 (SAS Institute, Inc., Cary, NC)

All toxicities will be graded on all patients that receive any amount of study drug. Only patients who receive 12 week of therapy will be used for final analysis. The dose escalation schema, definition of DLT, and endpoints are in section 5.

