1.5.2 Evaluation of Response

All patients included in the study must be assessed for response to treatment, even if there are major protocol treatment deviations or if they are ineligible. Each patient will be assigned one of the following categories: 1) complete response, 2) partial response, 3) stable disease, 4) progressive disease, 5) early death from malignant disease, 6) early death from toxicity, 7) early death because of other cause, or 9) unknown (not assessable, insufficient data). [Note: By arbitrary convention, category 9 usually designates the “unknown” status of any type of data in a clinical database.]

All of the patients who met the eligibility criteria (with the possible exception of those who received no study medication) should be included in the main analysis of the response rate. Patients in response categories 4-9 should be considered to have a treatment failure (disease progression). Thus, an incorrect treatment schedule or drug administration does not result in exclusion from the analysis of the response rate. Precise definitions for categories 4-9 will be protocol specific.

All conclusions should be based on all eligible patients. Subanalyses may then be performed on the basis of a subset of patients, excluding those for whom major protocol deviations have been identified (e.g., early death due to other reasons, early discontinuation of treatment, major protocol violations, etc.). However, these sub analyses may not serve as the basis for drawing conclusions

concerning treatment efficacy, and the reasons for excluding patients from the analysis should be clearly reported. The 95% confidence intervals should also be provided.

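### PFS counts any later death on its own date while imaging is scheduled only on study, so progression unseen after stopping is dated too late; the direction and size of the effect on PFS rates depend on why patients stop and on follow-up

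*SAP*

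**What the plan says.** The event definition in SAP 1.1 is: "PFS will be defined as the time between date of first dose of the study therapy and date of progression or death, whichever occurs first". Two censoring rules follow, and both cover survivors only: "Patients will be censored on the date of last tumor assessment if they remain alive and do not have tumor progression" and "Surviving patients who did not receive any on-treatment tumor assessment will be censored on the date of first dose of study medication". PFS rates at fixed time points come from the Kaplan-Meier curve. A one-week window before each time point allows for scan dates; it does not limit late deaths.

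The calendar in Protocol section 6 marks brain/spine MRI at pre-study and week 12. Its footnote c reads "Continue pattern of measurements while on study". In the text available, the MRI row has no mark in the Off Study column, whereas the ECG row has one. Protocol section 3 adds: "No investigational or commercial agents or therapies other than those described below may be administered with the intent to treat the patient's malignancy". A child who needs other antitumor treatment must therefore leave protocol therapy.

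Two statements about the analysis population bear on this. SAP 1.1 says "Only patients who receive 12 week of therapy will be used for final analysis", while SAP 1.5.2, on response, says "All conclusions should be based on all eligible patients".

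**The concern.** Once a child stops, the plan no longer schedules the scan that would show progression, but it still counts death whenever it comes. If the tumor progresses unseen in between, the time from progression to death is recorded as progression-free time, including any time gained from later treatment.

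This is foreseeable here. Protocol 2.1.6 asks only for a life expectancy above 8 weeks, and the first on-treatment MRI is at week 12. Objective 1.2.2 (2- and 5-year survival) means that late deaths should be known.

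PFS is a planned descriptive analysis and is not named in any objective. It could inform objective 1.2.3, the recommendation on larger studies. Objective 1.2.1 concerns response and toxicity, and overall survival is unaffected.

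**Working it through.** The SAP gives no PFS rate, median or event count, so there is no PFS figure to reproduce. Its only computed figures, the 80% response intervals, do not enter this point.

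**Step 1. What the rules do to a patient who stops with no recorded progression**

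| Status at analysis | Recorded PFS |
|---|---|
| Died, at any interval and after any therapy | Event on the death date |
| Alive, at least one on-treatment scan | Censored at last assessment |
| Alive, no on-treatment scan | Censored at first dose |

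**Step 2. One child.** Stable scan at week 12, deterioration and stop at week 18, no further scan, death 52 weeks later. Recorded PFS = 18 + 52 = 70 weeks. If true progression was at week 18, this is 52 weeks too long.

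**Step 3. That child in a curve of 20** (the planned size, SAP 1.2). For illustration, let the other 19 all have observed events, 10 of them after week 12 and 4 after week 24. The 24-week rate is:
- truth, progression at week 18: 4/20 = 20%;
- SAP rule, child has died: 5/20 = 25%;
- SAP rule, child alive and censored just after week 12: (11/20) × (4/10) = 22%.

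Now take a child who stops without progressing and would have stayed progression-free past week 24. The truth is 5/20 = 25%. If alive and censored just after week 12, the curve gives 22%; if censored at first dose, 4/19 = 21%. The same set of rules can therefore push the rate either way.

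**Step 4. Upper range for deaths after a week-18 stop.** Assume exponential survival after the stop with median m weeks (not in the documents). The share still counted progression-free at week 24 is 2^(-6/m):

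| m (weeks) | 13 | 16 | 26 | 52 |
|---|---|---|---|---|
| Share | 0.73 | 0.77 | 0.85 | 0.92 |

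If all these children had truly progressed by week 18 and all have died by the analysis, the 24-week rate is overstated by (fraction stopping this way) × share. For 10% of patients (2 of 20) that is 7.3 to 9.2 points; for 20% (4 of 20), 14.5 to 18.5 points.

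**Step 5. The whole curve, deaths and censoring together.** Simulation with 200,000 patients per scenario. All inputs are assumptions: exponential PFS with median 9, 17 or 26 weeks, paired with median survival after progression of 13, 26 or 52 weeks; 15% or 40% of patients prone to stop without documented progression; scans every 12 weeks on treatment. The middle column is the range over all scenarios. The last column is the case with medians 17/26 and 40% prone.

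| Stopping pattern, data cutoff | 24-week rate, SAP minus true (points) | Example: SAP vs true |
|---|---|---|
| Random, 30 weeks | -4.4 to -0.4 | 33.5% vs 37.7% |
| Random, 40 weeks | -3.6 to +1.6 | 35.6% vs 37.7% |
| Random, 52 weeks | -2.2 to +3.9 | 37.8% vs 37.5% |
| Random, 104 weeks | +0.8 to +6.9 | 43.6% vs 37.6% |
| Within 2 weeks before progression, 104 weeks | +5.9 to +16.8 | 54.3% vs 37.5% |

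Would a different rule alone cure this? In the two 104-week examples, censoring all stoppers at the last scan gives 33.5% (random) and 52.0% (just before progression). Counting a death only within 24 weeks of the last scan gives 32.8% and 47.8%. Neither recovers the truth in both settings. In the last row censoring is still 52.0 - 37.5 = 14.5 points too high, so most of that error comes from the progression not being seen.

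**Step 6. Stops before week 12.** If the 12-week sentence does not govern PFS, a child who stops at week 6 for deterioration (m = 16) is still counted progression-free with probability 2^(-6/16) = 0.77 at week 12 and 2^(-18/16) = 0.46 at week 24. If the sentence does govern PFS, these children are not in the curve. In the same simulations, keeping only patients with 12 weeks on therapy gives a 24-week rate of 40-74% against a true 16-38%. That shift exceeds the one from late deaths in every scenario where both were run.

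**The case against.** A reader might infer that PFS for every early stopper turns into survival on later treatment and that the estimate is therefore certainly too high. The documents do not support that. The late date applies only to stoppers who die without recorded progression. Surviving stoppers are cut back to the last scan or to first dose and enter the same curve. The supplied text does not fix follow-up at analysis: SAP 1.1 says only that analysis follows completion of the study and accrual. At 20 patients and 10 per year, accrual takes about 2 years, so follow-up could range from very short to about 104 weeks at the end of accrual. The zero and downward results in step 5 all come from random stopping with cutoffs of 52 weeks or less.

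A reader might also infer that the plan has no event for clinical progression. That cannot be shown: the SAP says progression without limiting it to scans, and the section with the tumor-evaluation definitions (Protocol 2.1.2 points to 10.1.2) is not in the supplied text. If documented clinical progression counts, the child in step 2 has an event at week 18 and the example falls away.

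Further points stand in part. Counting every death whatever therapy followed is a recognized treatment-policy definition, but it works as intended only if progression is still looked for after stopping. The missing Off Study MRI is one empty cell in a table read by a program, and on study need not mean on treatment; the original table should be checked. The trial is also small: at a 40% rate with 20 patients, the 95% half-width is 1.96 × √(0.4 × 0.6/20) = 21 points, which exceeds the biases in step 5. That limits how much PFS can carry, but sampling error does not excuse a systematic one.

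**Conclusion.** The point holds in limited form. On the text, a patient who stops without recorded progression, progresses unseen and later dies has a PFS event dated too late, by the whole interval from progression to death. For the PFS rate, the bias is upward when stopping reflects deterioration and follow-up is long (+5.9 to +16.8 points at 24 weeks in the scenarios run). It is smaller with random stopping and long follow-up (+0.8 to +6.9), and nil or downward in several short-follow-up scenarios (as low as -4.4). These sizes rest on assumed stopping patterns and survival times that the documents do not give; they show direction and range, not an expected value.

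Whether children who stop before week 12 are affected depends on whether the 12-week sentence governs PFS, which the SAP does not say. The correction is worth making because it is cheap and improves event dates. It does not threaten a named objective.

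**What to change.** 1. For patients who stop without progression, collect the stop date and reason, the start date of any new antitumor therapy, and the dates and results of routine-care MRIs until progression or death. Use these to date PFS events. No extra procedures are needed.
2. Keep the current PFS rule as primary. Add a sensitivity analysis that dates the event at treatment stop, or at start of new therapy, when death follows with no tumor assessment in between. It belongs in a sensitivity analysis because it errs early for children who stop for other reasons.
3. State whether progression includes documented clinical progression and, if so, report scan-only PFS alongside, since clinical progression is more subjective.
4. State whether the 12-week sentence in SAP 1.1 applies to PFS, and reconcile it with the all-eligible-patients rule in SAP 1.5.2.

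Cost: SAP wording and a few case report form fields. PFS may look less favorable as a result.

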6. STUDY CALENDAR

Baseline evaluations are to be conducted within 2 weeks prior to start of protocol therapy. Scans and x-rays must be done ≤ 4 weeks prior to the start of therapy. In the event that the patient's condition is deteriorating, laboratory evaluations should be repeated within 48 hours prior to initiation of the next cycle of therapy.

Timing of protocol therapy administration and response assessment studies are based on schedules derived from the experimental design or on established standards of care. Minor unavoidable departures (up to 72 hours) from protocol directed therapy and/or disease evaluations for valid clinical, patient and family logistical, or facility, procedure and/or anesthesia scheduling issues are acceptable (except where explicitly prohibited within the protocol).

Procedure	Pre-Study	Wk 1	Wk 2	Wk 3	Wk 4	Wk 5	Wk 6	Wk 7	Wk 8	Wk 9	Wk 10	Wk 11	Wk 12 ^c	Off Study ^d
Informed consent	X													
Lenalidomide		A	A	A		A	A	A		A	A	A		
Vorinostat		B		B		B		B		B		B		
Demographics	X													
Medical history	X													
Concurrent meds	X	X-----X												
Physical exam	X	X		X		X		X		X		X		X
Vital signs	X	X		X		X		X		X		X		X
Height	X	X		X		X		X		X		X		X
Weight	X	X		X		X		X		X		X		X
Performance status	X	X		X		X		X		X		X		X
CBC w/diff, plts	X	X		X		X		X		X		X		X
Serum chemistry ^a	X	X		X		X		X		X		X		X
ECG	X												X	x
MRI brain/spine ^e	X												X	
Adverse event		X-----X											X	

evaluation														
B-HCG	X ^b	X ^b	X ^b	X ^b	X ^b				X ^b				X ^b	

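### PFS drops living patients with no on-treatment scan at day 0; with the first scheduled MRI at week 12 this can overstate PFS if they failed more often, and the plan has no check for it

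*SAP*

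**What the plan says.** SAP 1.1 defines the endpoint: "PFS will be defined as the time between date of first dose of the study therapy and date of progression or death, whichever occurs first". Two censoring rules follow. The general one is "Patients will be censored on the date of last tumor assessment if they remain alive and do not have tumor progression". The special one is "Surviving patients who did not receive any on-treatment tumor assessment will be censored on the date of first dose of study medication". Only the general rule says in words that the patient must be free of progression. On estimation, the SAP says: "Progression free survival (PFS) and overall survival rates and the corresponding confidence intervals at fixed time points will be derived from the Kaplan Meier estimate". It does not name the time points.

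In the Protocol 6 calendar, the "MRI brain/spine" row is marked at Pre-Study and week 12, and its Off Study cell is empty. The ECG row just above it does carry an Off Study mark. Footnote c continues the pattern while the patient is on study. Footnote e makes the MRI depend on diagnosis and tumor location.

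SAP 1.5.2 includes among its response categories "9) unknown (not assessable, insufficient data" and rules: "Patients in response categories 4-9 should be considered to have a treatment failure (disease progression". That rule sits in the paragraph on eligible patients who "should be included in the main analysis of the response rate".

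The last paragraph of SAP 1.1 restricts the final analysis to patients who receive 12 weeks of therapy. SAP 1.5.2 wants conclusions drawn from every eligible patient.

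**The concern.** Protocol 2.1.6 admits patients with a life expectancy of more than 8 weeks, and the first scheduled on-treatment scan is at week 12. Patients who leave before that scan are therefore foreseeable. Those still alive at analysis get zero PFS follow-up and leave the risk set before the first event. In recurrent or refractory CNS tumors, stopping early may often mean progression. If so, the censoring is informative and the curve mainly describes patients well enough to reach the scan.

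With about 20 patients, a handful of such cases can move the estimate by 10 points or more. Protocol 1.2.3 wants efficacy data on which to recommend larger studies, so a PFS figure from this trial may be carried forward. The plan asks for neither a count of these patients nor a second analysis that treats them differently.

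**Working it through.** The plan states no PFS rate, PFS time point or expected number of unscanned patients, so it has no figure to reproduce.

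**Inputs**
- N = 20 (SAP 1.2, approximate).
- Week 12 as the illustrative time point (first scheduled MRI, Protocol 6).
- k = number of living patients never scanned on treatment. Assumed.
- s = number of scanned patients progression-free at week 12. Assumed.
- Simplification: the other 20 − k patients are all assessed at week 12, with no other censoring before then.

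**Formula.** A patient censored at time 0 is never at risk when an event occurs. Kaplan-Meier at week 12 is then 1 − (20 − k − s)/(20 − k) = s/(20 − k). If the k patients all failed before week 12, the true share is s/20, and the overstatement factor is 20/(20 − k): 1.11, 1.25 and 1.43 for k = 2, 4 and 6.

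**Size if all k progressed**

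| k | true 10/20 = 50% | true 8/20 = 40% |
|---|---|---|
| 2 | 10/18 = 55.6% | 8/18 = 44.4% |
| 4 | 10/16 = 62.5% | 8/16 = 50.0% |
| 6 | 10/14 = 71.4% | 8/14 = 57.1% |

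**Direction.** Take k = 6, with 7 of the 14 scanned patients progression-free. The day-0 rule gives 7/14 = 50% whatever happened to the other six. The true figure depends on them:
- all 6 failed: 7/20 = 35%, so PFS is overstated by 15 points;
- 3 of 6 failed, the same rate as scanned patients: 10/20 = 50%, no bias;
- none failed: 13/20 = 65%, so PFS is understated by 15 points.

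**Deaths.** The day-0 rule covers survivors only. Keep the six as early failures (true 12-week PFS 35%):
- all alive at analysis: 7/14 = 50%;
- three dead at week 8, three alive: (14/17) × (7/14) = 7/17 = 41.2%;
- all dead at week 8: (14/20) × (7/14) = 35%, no inflation;
- all dead at week 20: 13/20 = 65% at week 12, then (13/20) × (7/13) = 35% at week 24. Here the early excess comes from dating the event at death, not from the day-0 rule.

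**The 12-week sentence.** Suppose it governs PFS and the 14 scanned patients are the completers. The six early leavers are then excluded whether alive or dead, and the result is 7/14 = 50% even in the case where all six died at week 8 and the full set gives 35%. Changing the censoring rule alone would not alter that result.

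**The case against.** The strongest reply has five parts.

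1. *Day-0 censoring of patients with no assessment is a common convention, and PFS is not among the objectives in Protocol 1.1 and 1.2.* Both points stand. PFS here is descriptive, with no decision rule attached. They limit the weight of the concern, but they do not make the number reported less sensitive to the rule.

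2. *The rule may already be narrower than it looks.* The PFS definition does not say that progression must be seen on a scan, and the preceding sentence censors only patients without progression. On that reading, clinical progression is already an event. This is possible. The special rule carries no such condition, however, and the section on measurable disease that Protocol 2.1.2 points to is not in the public text. The wording needs settling.

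3. *Few patients may be affected.* Deaths remain events, the analysis takes place after accrual of about two years (20 patients at 10 per year), and footnote e leaves room for other imaging. This stands, and it is why the size is unknown.

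4. *A reader might infer that SAP 1.5.2 contradicts the PFS rule by declaring the same patient progressed.* The documents do not support that. Section 1.5.2 governs the response rate, where counting a non-assessable patient as a failure fixes the denominator. It never mentions PFS, and it leaves the exact definitions of categories 4 to 9 to the protocol. The two endpoints handle the same missing scan differently, which is an inconsistency between endpoints only.

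5. *A reader might also infer that the rule removes early failures and so inflates PFS as a matter of course.* That goes too far. It affects only those alive and never scanned, and in a dose-escalation study patients may also leave for toxicity or withdrawal. The direction depends on why they left.

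**Conclusion.** The concern holds in a conditional form. Living patients with no on-treatment scan contribute nothing to PFS, and the calendar makes such patients foreseeable. If they failed more often than scanned patients, which is plausible here but not certain, PFS is overstated: by about 6, 13 or 21 points for k = 2, 4 or 6, assuming 20 patients, a true 12-week PFS of 50%, and that all k progressed and are alive at analysis. With equal failure rates the bias is nil, and with a lower failure rate it reverses.

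The 12-week completer sentence belongs to the same problem. It may drop the same patients by another route, it would also drop patients who died early, and it conflicts with the all-eligible principle of SAP 1.5.2. The censoring rule and the analysis set need to be settled together.

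**What to change.** 1. Define the PFS set as all treated eligible patients, and reword the 12-week sentence in SAP 1.1 so that it agrees with this and with SAP 1.5.2.
2. State that the day-0 rule applies only to survivors with neither an on-treatment assessment nor documented progression, and say what documentation counts. Physical exam and performance status are already marked at the off-study visit.
3. Add a sensitivity analysis that counts every unscanned survivor as an event at last on-treatment contact, and show it beside the day-0-censored estimate. It is a lower bound on how these patients could affect PFS. It should not replace the main estimate, because counting all of them as events could bias PFS downward.
4. Report the number of patients censored at day 0, with reasons for leaving.

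The cost is SAP wording, one extra Kaplan-Meier run and one line in the disposition table; no new procedure is needed. The downsides are a softer date for events not seen on a scan and a second, less favourable PFS figure in the report.

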1.4 Analysis of Secondary Endpoints

Responses will be reported as a secondary endpoint. Every report should contain all patients included in the study. For the response calculation, the report should contain at least a section with all eligible patients. Another section of the report may detail the response rate for evaluable patients only. However, a response rate analysis based on a subset of patients must explain which patients were excluded and for which reasons. It is preferred that 95% confidence limits are given.

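### The SAP limits its final analysis to patients who received 12 weeks of therapy, against its own all-eligible-patients rule; if followed, this biases the efficacy estimates upward

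*SAP*

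**What the plan says.** The last paragraph of SAP 1.1 first keeps toxicity grading on everyone given any study drug. It then states, without qualification: "Only patients who receive 12 week of therapy will be used for final analysis". The term final analysis is not defined.

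Other parts of the SAP point the other way:

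- **SAP 1.5.2:** "All conclusions should be based on all eligible patients". Eligible patients belong in the main response analysis, with a possible exception for those never dosed. Categories 4 to 9 (progression, the three kinds of early death, unknown) count as treatment failures. Subsets that leave out patients who stopped treatment early are allowed, but "these sub analyses may not serve as the basis for drawing conclusions" on efficacy.
- **SAP 1.4:** "For the response calculation, the report should contain at least a section with all eligible patients".
- **SAP 1.1, earlier in the same section:** "We will describe the baseline demographic and clinical characteristics, adverse events and response in all patients". For PFS: "Surviving patients who did not receive any on-treatment tumor assessment will be censored on the date of first dose of study medication".

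**The concern.** Completing 12 weeks of therapy is a post-baseline outcome, closely tied to the endpoints being estimated. A patient who dies, progresses clinically or cannot tolerate treatment before week 12 is excluded because of what happened on study.

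Such patients are foreseeable. Protocol 2.1.6 asks only for an expected survival of more than eight weeks, which is shorter than the 12-week condition.

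The stakes are the efficacy results. Response is a primary objective in Protocol 1.1.2. Protocol 1.2.1 to 1.2.3 add a comparison of response with historical controls, 2- and 5-year survival, and data to support larger studies. With about 20 patients and no control arm, the choice of denominator can change the reported result substantially. As the SAP stands, an analyst could cite it for either population.

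Toxicity is not affected: SAP 1.1 and 1.5.1 keep all treated patients. No claim is made here about DLT counts or dose escalation.

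**Working it through.** **Step 1. The rules side by side**

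| Item | SAP 1.1 restriction | Elsewhere in the SAP |
|---|---|---|
| Response denominator | Patients with 12 weeks of therapy | All eligible (1.4, 1.5.2); all patients (1.1) |
| Early progression, early death, unknown | Excluded if therapy ended before week 12 | Counted as failures (1.5.2) |
| Subset without early stoppers | Is the final analysis | Cannot support efficacy conclusions (1.5.2) |
| PFS and OS set | Patients with 12 weeks of therapy | Not stated; the PFS censoring rule implies a wider set |

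The last row follows from the Protocol section 6 calendar. The row "MRI brain/spine ^e" is marked before study and at week 12, with nothing between. A surviving patient with no on-treatment scan is therefore mainly one who left before week 12. A rule that censors such patients at first dose has little use if they are already excluded.

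**Step 2. Direction**

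- *PFS and OS.* PFS runs from first dose (SAP 1.1). No origin is stated for OS, so first dose is assumed. Requiring 12 weeks of therapy removes every death before week 12 and every early progressor who stops. Both estimates rise.
- *Response.* Completer rate ÷ all-patient rate = P(complete | responder) ÷ P(complete). The bias is upward whenever responders complete more often than the group as a whole.

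**Step 3. Size**

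The plan gives no completion rate, median PFS or median OS, so there is no figure of its own to reproduce. Only n = 20 comes from the documents (SAP 1.2). The stopping rates, medians and exponential form are assumptions.

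*Response: two responders, both complete (exact Clopper-Pearson 95% intervals)*

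| Stop before week 12 | Rate | 95% CI |
|---|---|---|
| None excluded | 2/20 = 10% | 1.2–31.7% |
| 20% (4 patients) | 2/16 = 12.5% | 1.6–38.3% |
| 60% (12 patients) | 2/8 = 25% | 3.2–65.1% |

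*PFS at 24 weeks.* S(t) = 0.5^(t/m), with m the median in weeks. Let f be the share of progressions before week 12 that end therapy before week 12; the rest are found at the week-12 MRI and stay in the set. Excluded = f(1 − S(12)). Reported = S(24) ÷ [1 − f(1 − S(12))].

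| m | True S(24) | f = 0.5: excluded | f = 0.5: reported | f = 1: excluded | f = 1: reported |
|---|---|---|---|---|---|
| 8 | 13% | 32% | 18% | 65% | 35% |
| 12 | 25% | 25% | 33% | 50% | 50% |
| 16 | 35% | 20% | 44% | 41% | 59% |
| 24 | 50% | 15% | 59% | 29% | 71% |

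For m = 12 and f = 0.5: S(12) = 0.50, S(24) = 0.25, and 0.25 ÷ (1 − 0.5 × 0.50) = 0.25 ÷ 0.75 = 33%. The f = 1 columns are close to an upper bound.

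*OS at 2 years (104 weeks), excluding only deaths before week 12.* Reported = S(104) ÷ S(12).

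| m | Excluded | True S(104) | Reported |
|---|---|---|---|
| 26 | 27% | 6.25% | 8.6% |
| 39 | 19% | 15.7% | 19.5% |
| 52 | 15% | 25.0% | 29.3% |

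The OS shift would be larger if stopping early also predicts later death, which this calculation leaves out.

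**The case against.** - **SAP 1.5.2 already governs response.** It bases conclusions on all eligible patients and bars subsets without early stoppers, so a careful analyst would not draw response conclusions from 12-week completers. This has force for response. However, no text gives 1.5.2 precedence over an unqualified sentence about the final analysis. Section 1.5.2 also deals with response, so PFS and OS remain open.
- **The sentence may only define evaluability.** The first on-study MRI is at week 12, SAP 1.4 allows an added section on evaluable patients, and the next sentence in SAP 1.1 refers to a section 5 for DLT and endpoints. That section is not in the text available here; Protocol section 5 covers adverse event reporting. The reading is possible, but the words do not say it. The fix allows for it.
- **Response need not be biased upward.** This is correct in principle. With 4 responders of 20, of whom 2 stop early, and 12 completers, the rate is 2/12 = 16.7% against 20%. But those responders would have to be documented before the only scheduled on-study scan, so this is an off-schedule exception.
- **The sizes are assumed and the OS shift is modest.** Both points stand. In these examples 2-year OS moves by about 2 to 4 percentage points, which is small beside the imprecision of about 20 patients. PFS is not a listed protocol objective, and 24 weeks is not a time point named in the plan.
- **The study is chiefly about safety, and SAP 1.4 calls response secondary.** The safety results are indeed untouched. Protocol 1.1.2 nevertheless lists response as primary, and the SAP commits to response, PFS and OS estimates.

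**Conclusion.** The concern holds, and the sentence must be changed before analysis. The contradiction can be read from the SAP alone and needs no assumed figure: one sentence makes final the kind of subset that 1.5.2 bars from supporting efficacy conclusions.

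The upward direction is firm for PFS and OS. For response it is the expected direction, on the condition that responders complete 12 weeks more often than other patients.

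The size cannot be derived from the documents. Under the stated assumptions, 24-week PFS rises by about 6 to 9 percentage points when half of early progressors stop before week 12, and by about 21 to 25 points in the near-limiting case. Two-year OS rises by about 2 to 4 points. A 10% response rate becomes 12.5% to 25%.

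**What to change.** Delete the sentence and state one analysis set per endpoint:

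- **Safety:** every patient given any study drug.
- **Response, main analysis:** all eligible patients, with the possible exception in 1.5.2 for those never dosed; categories 4 to 9 are failures.
- **PFS and OS:** every patient given at least one dose, with time counted from first dose. This matches the PFS origin already in SAP 1.1 and supplies the missing OS origin. The set may include treated patients later found ineligible, so the SAP should say that this is intended.
- **Patients completing 12 weeks of therapy:** supportive analysis only, not a basis for efficacy conclusions.

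If the sentence was meant as an evaluability rule for another purpose, reconcile it with the section 5 that SAP 1.1 cites, and limit it to that purpose.

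The cost is SAP wording plus that cross-check. The reported efficacy may be less favourable than under the 12-week restriction.
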